2.4.2. Benefit Assessment

The study population enrolled in this study has a high-unmet medical need. Participants failing multiple lines of prior treatments do not have many therapeutic options left, and if response can be achieved with currently available drugs, it is usually of short duration. This study is being performed to study safety and pharmacokinetics data in participants who have been previously treated with multiple agents, including alkylator, PI and immunomodulatory imide drug.

Data from single-agent study BMA117159 support further evaluation of participants with MM failing currently available treatments.

Based on the available clinical data, and since 2.5 mg/kg has been selected as the recommended dose in the belantamab mafodotin clinical development program, (and as the dose approved in the U.S.A. and Europe), the 3.4 mg/kg dose may not be used in this study.

2.4.3. Overall Benefit: Risk Conclusion

Considering the measures taken to minimize risk to participants, the potential risks associated with belantamab mafodotin are justified by the anticipated benefits that may be afforded to participants with RRMM.

3. OBJECTIVES AND ENDPOINTS

Objectives	Endpoints		
Primary Objectives			
To determine safety and tolerability of belantamab mafodotin in Chinese Participants with RRMM	Adverse events (AE), i.e., number (%) of participants with DLTs, number (%) of participants with AEs		
Secondary Objectives	Secondary Objectives		
To evaluate PK profile of belantamab mafodotin in Chinese Participants with RRMM	ADC, total antibody and cys-mcMMAF PK parameters following IV single and repeat dose administration during dose escalation as data permit (e.g., AUC, Cmax, tmax)		
To evaluate safety and tolerability of belantamab mafodotin	Changes in clinical signs and laboratory parameters, ocular findings on ophthalmic exam		

Objectives	Endpoints
To evaluate the clinical measures of efficacy of belantamab mafodotin	ORR, defined as the percentage of participants with a confirmed partial response (PR) or better (i.e., VGPR, CR and stringent complete response [sCR]), according to the International Myeloma Working Group (IMWG) Response Criteria.
To assess anti-drug antibody (ADA) formation after IV single and repeat dose administration of belantamab mafodotin	Incidence and titers of ADAs against belantamab mafodotin
Participant self-reported symptomatic adverse effects by evaluation of tolerability of belantamab mafodotin	Symptomatic adverse effects and related impacts as measured by the OSDI
Exploratory Objectives	

4. STUDY DESIGN

4.1. Overall Design

This is a phase I, open-label dose-escalation study to explore safety, PK, tolerability, immunogenicity and clinical activity of belantamab mafodotin monotherapy in Chinese participants with RRMM. The study will enroll up to 12 evaluable participants (For study schematic refer Figure 1). This study will include two dose cohorts. Up to six evaluable participants are expected for each cohort and the actual numbers will depend on the safety observed. Each participant will be involved in the study until participant have progressed, died, withdrawn consent, discontinued treatment due to other reasons, or have been lost to follow-up.

4.1.1. Planned Dose Levels

Projected dose levels are 2.5 mg/kg and 3.4 mg/kg. De-escalation to 1.9 mg/kg will be allowed in case of \geq 2 DLT at dose 2.5 mg/kg. No doses will be explored beyond 3.4 mg/kg, the dose that is considered to be the Maximum Feasible Dose (MFD).

Dose-escalation will follow a 3 + 3 dose-escalation procedure as shown in Table 2. Evaluation of available safety data from at least 3 participants that have completed a minimum of 21 days is required prior to defining a new dose level and to start the next dose cohort. There will be no intra-participant dose escalation. The first 3 participants in 2.5 mg/kg dose group will receive the study treatment sequentially with an observation window of 7 days, to observe acute toxicities. If the participating investigator and the coordinating investigator see no potential safety concerns from the first participant, the participanting investigator and the coordinating investigator may recommend to enrol the next participant. Participants should not be enrolled at a higher dose level until at least 3-6 participants in the previous dose cohort complete 21 days of post-dose assessment.

Table 2 3 + 3 Dose-Escalation Guidelines

Number of Participants with DLT at a Given Dose Level	Action	
0 out of 3 Participants	Escalate to next dose level and enter 3 Participants	
1 out of 3 Participants	Accrue 3 additional evaluable Participants at current dose level for a total of 6 evaluable Participants	
	 If 0 of the 3 Participants experience a dose-limiting toxicity (DLT), proceed to next dose level. If 1 or more Participants experience a DLT, dose will be de-escalated to 1.9 mg/kg if the current dose cohort is 2.5 mg/kg, otherwise the dose-escalation is stopped and this dose is declared the maximum tolerated dose (MTD). 	
1 out of 6 Participants	Escalate to next dose level	
2 or more Participants in a dosing cohort (up to 6	Dose will be de-escalated to 1.9 mg/kg if the	
Participants)	current dose cohort is 2.5 mg/kg, otherwise dose- escalation will be stopped. At this dose level, the MTD has been exceeded (highest dose administered).	

Up to 6 participants will be enrolled into each of these dose levels with the above dose escalation rule followed.

As per current available safety and efficacy information of belantamab mafodotin studies, the 3.4 mg/kg dose cohort is converted to an optional cohort in the dose-escalation study design. Escalation may not proceed if not supported by emerging clinical data from other belantamab mafodotin studies.

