Preliminary clinical data from the global ongoing BMA117159 study as of the data cut off of 31 Aug 2018, a total of 73 participants with RRMM have been treated with at least one dose of belantamab mafodotin. The Part 1 dose-escalation phase enrolled 38 participants at doses ranging from 0.03 mg/kg IV up to 4.6 mg/kg IV. Belantamab mafodotin was well tolerated with no DLTs up to 4.6 mg/kg q3w; MTD was not reached. The Part 2 dose expansion phase has enrolled 35 participants with MM at the recommended Phase 2 dose (RP2D) of 3.4 mg/kg IV, O3W and has demonstrated an objective response rate (ORR) of 60% [95% confidence interval (CI): 42.1%, 76.1%], in heavily pre-treated participants with relapsed/refractory multiple myeloma (RRMM). The median duration of response (DOR) was 14.3 months [95% CI: 10.6, NA]; the median progression free survival (PFS) in this population was 12.0 months [95% CI: 3.1, not evaluable [NE]. Overall, belantamab mafodotin has a manageable safety profile with thrombocytopenia/platelet count decreased and corneal events as the most commonly reported events. Based on these data, GSK has initiated Study 205678, a global phase II study evaluating the safety and efficacy of belantamab mafodotin monotherapy (3.4 and 2.5 mg/kg administered once every 3 weeks) in participants with relapsed / refractory multiple myeloma previously treated with at least 3 classes of drugs, including PIs, IMIDs and an anti-CD38 antibody, and who have demonstrated disease progression on or within 60 days of completion of the last therapy.

Study 208465 is designed to evaluate the safety, tolerability, PK, immunogenicity and clinical activity of belantamab mafodotin in Chinese participants with RRMM who have received at least 2 prior line of anti-myeloma therapy including an alkylator, a proteasome inhibitor (PI) and an immunomodulatory agent (IMiD).

Objectives and Endpoints:

Objectives	Endpoints
Primary Objectives	
To determine safety and tolerability of belantamab mafodotin in Chinese Participants with RRMM	Adverse events (AE), i.e., number (%) of participants with DLTs, number (%) of participants with AEs
Secondary Objectives	
To evaluate PK profile of belantamab mafodotin in Chinese Participants with RRMM	ADC, total antibody and cys-mcMMAF PK parameters following IV single and repeat dose administration during dose escalation as data permit (e.g., AUC, Cmax, tmax)

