Number of Participants: No formal statistical hypotheses are being tested. Analysis of the data obtained will only utilise descriptive methods. The sample size planned arises from the predefined dose escalation criteria for dose selection and is not driven by statistical considerations. Based on the 3+3 dose escalation design the anticipated size will be up to 6 evaluable participants for each dose level. The dose escalation decisions will be based on the recommendation from the Dose Escalation Meeting as well as the totality of the safety, tolerability and pharmacokinetics.

Intervention Groups and Duration:

Belantamab mafodotin will be administered via 30-60 min intravenous (IV) infusion once every three weeks on day 1. Participants will be treated until disease progression, intolerable toxicity, end of study or informed consent withdrawal.

Treatment Arms

Dose escalation will characterize the safety, tolerability and immunogenicity of escalating doses of belantamab mafodotin. The following dose levels of belantamab mafodotin are planned to be studied: 2.5 mg/kg and 3.4 mg/kg.

Data Monitoring Committee: No

Dose Escalation Meeting: Yes

Inclusion Criteria

Participants are eligible to be included in the study only if all of the following criteria apply:

- 1. Provide signed written informed consent, which includes compliance with requirements and restrictions listed in the consent form
- 2. Male or female, 18 years or older (at the time consent is obtained)
- 3. Eastern Cooperative Oncology Group (ECOG) performance status of 0-2
- 4. Histological or cytologically confirmed diagnosis of MM as defined according to IMWG, 2014 criteria and
 - a. Has undergone autologous stem cell transplant or transplant is considered not feasible by local assessment.
 - b. Has failed at least 2 prior lines of anti-myeloma treatments, containing ALL of the following classes of drugs: alkylating agent, IMID and PI.
 - c. In addition, eligible participants needs to be refractory to an IMiD (i.e., lenalidomide or pomalidomide), and to a proteasome inhibitor (i.e., bortezomib, ixazomib or carfizomib) as defined by IMWG criteria.
 - d. Participants who failed with CD38 antibody (i.e., daratumumab) in previous clinical trials can also be considered to include if they meet the remainder of inclusion criteria in this protocol.

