4.2. Scientific Rationale for Study Design

Participants with RRMM who have experienced relapse after previous treatment with alkylators, PI and immunomodulatory imide drug represent a population of unmet

medical need in China, for whom there is no approved treatment options. Given the clinical activity demonstrated in the BMA117159 study, the treatment with belantamab mafodotin might offer a benefit to this participant population. It is also expected that due to its unique mechanism of action, belantamab mafodotin may be able to overcome the resistance to previously used drugs in the RRMM population in China.

BMA117159 study has evaluated the safety and tolerability of belantamab mafodotin at doses ranging from 0.03 mg/kg IV up to 4.6 mg/kg IV. Belantamab mafodotin was well tolerated with no DLTs up to 4.6 mg/kg q3w; MTD was not reached, however, there was limited tolerability of the 4.6 mg/kg dose (prolonged fever, headache, severe fatigue). The maximum clinical benefit (ORR 60%) was observed at the 3.4 mg/kg dose level, but a significant number of participants required dose delays and dose reductions. At lower dose levels, the results were variable, with wide confidence intervals. Based on these data, GSK has initiated Study 205678, a global phase II study evaluating the safety and efficacy of belantamab mafodotin monotherapy (3.4 and 2.5 mg/kg administered once every 3 weeks) in participants with relapsed / refractory multiple myeloma. As the safety profile of belantamab mafodotin is established in a predominantly Caucasian MM population, the primary objective of study 208465 is to evaluate safety and confirm appropriate dose for Chinese MM population. Given that there is no apparent evidence showing racial difference in MM and BCMA expression between Chinese and Western populations, global Phase II study selected dose (2.5 and 3.4 mg/kg) will be investigated in study 208465.

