9.5.2. Dose Escalation Committee (DEC)

The Dose Escalation Committee (DEC) will monitor intervention-emergent data on an ongoing basis throughout study conduct for the purpose of ensuring the continued safety

of participants enrolled in this study as described in the Dose Escalation Plan. The DEC will be chaired by the GSK medical monitor and membership will include a GSK clinical scientist, GSK safety physician, GSK statistician, GSK pharmacokineticist, along with additional GSK staff as appropriate and all participating investigators.

The DEC will review of relevant safety, PK, and PD data generated immediately after all participants treated in the same dose cohort have passed the DLT period.

Dose Escalation Meetings will be scheduled at the conclusion of the DLT assessment period for participants enrolled in each cohort to review safety data and determine the next dose level appropriate for study.

In addition, throughout the conduct of the study the DEC may decide to:

- 1) Modify the dose escalation of belantamab mafodotin proposed by the 3+3 model based on clinical judgement.
- 2) Investigate alternative dosing regimens
- 3) Modify the timing, frequency, and/or type of safety assessments performed during study conduct
- 4) Approve continuation of belantamab mafodotin study therapy in participants who have experienced DLT provided the toxicity did not meet study discontinuation criteria and has resolved at the time of re-start.
- 5) Request intervention of additional participants at previously completed dose levels for the purpose of obtaining additional safety, PK, PD, metabolite, or biomarker data (i.e. PK/PD/Metabolite).
- 6) Halt enrolment into any cohorts as deemed appropriate based on emerging clinical data at any time during the trial.

Dose escalation decisions will be made with DEC members after review of available safety data from at least one cycle of therapy with belantamab mafodotin. Available data will be provided to participants prior to each scheduled Dose Escalation Meeting. Attendees of Dose Escalation Meetings will include but not limited to DEC members. All dose escalation and safety decision will be documented in writing with copies maintained by GSK in the Trial Master File and submitted to each site for documentation. Decisions with potential impact on the safety of study participants (i.e., unfavorable change in risk/benefit assessment) will be promptly communicated to regulatory authorities and study sites as appropriate.

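### Protocol Table 2 labels one DLT result in a 3.4 or 1.9 mg/kg cohort both as the MTD and as above the MTD

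*Protocol*

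**What the plan says.** Table 2 in Protocol Section 4.1.1 has four rows, by number of participants with a DLT: 0 of 3, 1 of 3, 1 of 6, and 2 or more in a cohort of up to 6. They are called rows 1 to 4 here.

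- Row 2 adds 3 participants after 1 DLT in 3. If 1 or more of those has a DLT, a 2.5 mg/kg cohort de-escalates to 1.9 mg/kg. For any other cohort, "otherwise the dose-escalation is stopped and this dose is declared the maximum tolerated dose (MTD".
- Row 4 also de-escalates a 2.5 mg/kg cohort to 1.9 mg/kg and stops escalation in any other cohort. It then adds: "At this dose level, the MTD has been exceeded (highest dose administered".

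The only other levels are 3.4 mg/kg, which is optional, and 1.9 mg/kg, which opens only after 2 or more DLTs at 2.5 mg/kg. Neither document defines the MTD or says which row prevails, and the SAP does not use the term.

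**The concern.** A dose cannot both be the MTD and exceed it. Row 4 fits the rest of the table, in which a cohort passes only with 0 of 3 or 1 of 6. Row 4 alone covers 2 DLTs in the first 3 and calls that dose too toxic. Row 2 would name as the MTD a dose with 2, 3 or even 4 DLTs in 6.

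What is at stake is the dose conclusion in the study report. Section 4.2 says that "the primary objective of study 208465 is to evaluate safety and confirm appropriate dose for Chinese MM population", so a reader may look to the report for a statement about the MTD, and the protocol supports two opposite ones.

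**Working it through.** **The plan's own figure.** Section 4.1 allows up to 12 evaluable participants. Two cohorts of up to 6 give 2 × 6 = 12, either 2.5 then 3.4 mg/kg or 2.5 then 1.9 mg/kg. The figure reproduces.

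**Every outcome against every row.**

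| DLTs in the cohort | Rows met | Do they agree? |
|---|---|---|
| 0 of 3 | 1 | Single row |
| 1 of 3, then 0 of 3 | 2 and 3 | Yes, go up |
| 1 of 3, then 1, 2 or 3 of 3 | 2 and 4 | Yes at 2.5 mg/kg; no at 3.4 and 1.9 mg/kg |
| 2 or 3 of 3 | 4 | Single row |

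The clash is confined to one outcome at two dose levels, but there it is unavoidable, since 1 plus at least 1 is at least 2.

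**How likely that outcome is.** The documents give no DLT rate for this population, so the rate p is assumed at 5%, 7.6%, 10% and 20%. The Synopsis reports of the first-in-human study: "Belantamab mafodotin was well tolerated with no DLTs up to 4.6 mg/kg q3w; MTD was not reached". If all 38 participants in its escalation part were evaluable (an assumption), 0 of 38 has a one-sided 95% upper limit of 1 − 0.05^(1/38) = 0.0758, or 7.6%. That pools doses from 0.03 mg/kg upwards, so it is a rough guide only. The 20% case is a stress case.

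- Conflicting outcome in an open cohort: B(p) = 3p(1 − p)² × [1 − (1 − p)³].
- Cohort fails: F(p) = 3p²(1 − p) + p³ + B(p).
- Trial level, 3.4 mg/kg not opened, equal rates at 2.5 and 1.9 mg/kg: F(p) × B(p).

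| p | P(1 of 3) | P(1 or more of next 3) | B | P(2 or more of first 3) | F | F × B |
|---|---|---|---|---|---|---|
| 5% | 0.1354 | 0.1426 | 0.0193 | 0.0073 | 0.0266 | 0.0005 |
| 7.6% | 0.1947 | 0.2111 | 0.0411 | 0.0165 | 0.0575 | 0.0024 |
| 10% | 0.2430 | 0.2710 | 0.0659 | 0.0280 | 0.0939 | 0.0062 |
| 20% | 0.3840 | 0.4880 | 0.1874 | 0.1040 | 0.2914 | 0.0546 |

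Products and sums were taken before rounding. Most conflicting results would be exactly 2 of 6: the share is P(1 of 3)² / B, or 95%, 92%, 90% and 79%.

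**If 3.4 mg/kg does open.** If it opened after every pass at 2.5 mg/kg, some second cohort would always open. At equal rates the trial-level chance is then (1 − F) × B + F × B = B. With 10% at 2.5 mg/kg and 20% at 3.4 mg/kg, the 3.4 mg/kg route alone gives (1 − 0.0939) × 0.1874 = 17.0%. These are upper cases, because 3.4 mg/kg is optional.

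**The case against.** The best defence is that nothing planned depends on the label. Both rows stop escalation, so exposure, DLT and AE counts and sample size are the same. The MTD is not an objective or endpoint (Protocol Section 3, SAP Section 2.2), and the SAP's only DLT table is the Cycle 1 summary (SAP Section 14.12.8). Dose decisions also rest on the "recommendation from the Dose Escalation Meeting as well as the totality of the safety, tolerability and pharmacokinetics". The 3.4 mg/kg cohort may never be used, and Amendment 3, written to keep two ongoing participants on treatment, suggests without proving that escalation was over. All of this stands and limits the weight of the point. None of it reconciles two opposite written conclusions.

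A reader might infer more in two ways.

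*That the plan has no way forward when 1.9 mg/kg passes.* Row 1 says "Escalate to next dose level and enter 3 Participants" and row 2 says "If 0 of the 3 Participants experience a dose-limiting toxicity (DLT), proceed to next dose level". From 1.9 mg/kg the next level is 2.5 mg/kg, which has already had 2 or more DLTs. The table does not spell out this end state. But Section 4.1 plans two cohorts, and 2.5 then 1.9 mg/kg uses both. Section 9.5.2 has Dose Escalation Meetings "determine the next dose level appropriate for study" and lets the committee depart from the 3 + 3 rule on clinical judgement or halt enrolment. This is a matter of clarity.

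*That the wrong label could carry a wrong dose forward.* Sections 2.3.2 and 2.4.2 show that the programme chose 2.5 mg/kg for comparable efficacy and better safety than 3.4 mg/kg. That choice did not come from an MTD found in this study.

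**Conclusion.** Table 2 is wrong as written, and the error is minor. It affects only the MTD conclusion after 1 of 3 and then 1 or more of 3, and only in a 3.4 or 1.9 mg/kg cohort. If neither cohort opened, the point is moot. Up to the rough 7.6% limit, the conflicting result has at most a 4.1% chance in a cohort that opens, and about 0.2% over the trial if 3.4 mg/kg is not opened. The 20% stress case gives 18.7% and 5.5%. These figures rest on assumed DLT rates, independence between participants and, at trial level, equal rates at 2.5 and 1.9 mg/kg. The contradiction itself needs no assumption.

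**What to change.** In row 2, replace the clause that declares the current dose the MTD with *the MTD has been exceeded at this dose*. If escalation is complete, one sentence in the clinical study report adopting that reading is enough. If only 2.5 mg/kg was opened, no action is needed. The cost is one clause or one sentence, with no change to participants, stopping probabilities, the maximum of 12 or any display.

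Optionally, add a note under the table that after de-escalation a pass at 1.9 mg/kg does not lead back to 2.5 mg/kg unless the Dose Escalation Committee decides otherwise.

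Do not define the MTD simply as the highest dose studied with no more than 1 DLT in 6. That would make 2.5 mg/kg the MTD when no higher dose had failed, and would relabel a passing 3.4 mg/kg dose that Sections 4.1.1 and 4.1.2.1 call the maximum feasible dose. Any definition should apply only once a higher dose has been exceeded. Otherwise the report should say that the MTD was not reached, as the Synopsis does for the first-in-human study.

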4.1.2. Dose-Limiting Toxicity

The DLT observation window will be 21 days (1 cycle). Any participant that received at least 1 dose of belantamab mafodotin will be evaluated for DLTs using NCI-CTCAE Version 5.0 [NCI, 2017]. If participants prematurely discontinue for reasons other than toxicity but prior to completion of DLT observation period, additional participants may be enrolled as replacement participants at the discretion of the Sponsor in consultation with the investigator.

An event will be considered a DLT if its relationship to the investigational agent cannot be ruled out, occurs within the DLT reporting period and meets 1 of the following criteria:

- a. Any Grade 3 or greater non-hematologic toxicity as described in NCI-CTCAE Version 5.0 [NCI, 2017], other than corneal events:
- Persists for >48 hours despite supportive treatment
- Leads to hospitalization
- b. Haematologic toxicity:
- Grade 3 or greater febrile neutropenia lasting >48 hours despite adequate treatment:
 - Grade 3 CCI
 Grade 4 CCI
 CCI This section contained Clinical Outcome Assessment data collection questionnaires or indices, which are protected by third party copyright laws and therefore have been excluded.
- Grade 4 thrombocytopenia
 CCI
 CCI
- c. Grade 4 per the modified corneal grading scale provided in Table 7.
- d. Liver toxicity meeting pre-specified GSK liver stopping criteria as outlined in Section 7.1.1.

A participant who develops a DLT will be allowed to continue study treatment if the toxicity did not meet pre-defined stopping criteria (Section 7.1)and recovered to Grade ≤1 within 14 days or after a longer recovery period if the investigator and medical monitor agree that for a given participant the potential benefits may outweigh the risks.

